### **4.2. Secondary Objectives and Hypotheses**

Secondary hypotheses for this trial are that cathflo activase supplementation for TSP:

1. Is safe
2. Does not inhibit pleurodesis
3. Reduces the incidence of recurrence of pleural effusion
4. Reduces the incidence of incomplete pleurodesis (presence of loculated effusions)
5. Shortens the time to achieve pleurodesis.
6. Does not increase pain associated with TSP
7. Improves the patient's subjective assessment of dyspnea
8. Does not prolong chest tube drainage or length of hospitalization
9. Is as cost-effective as TSP alone

Secondary objectives for this trial are:

1. To determine if giving cathflo activase with TSP is associated with a higher incidence of complications compared to TSP with placebo.
2. To determine if giving cathflo activase with TSP improves pleural fluid drainage compared to TSP with placebo.
3. To determine if giving cathflo activase with TSP is associated with a greater decline in serum Hemoglobin and/or incidence of blood transfusion compared to TSP with placebo.
4. To determine if giving cathflo activase with TSP is associated with an increased incidence of repeat pleurodesis compared to TSP with placebo.
5. To determine if giving cathflo activase with TSP is associated with a lower incidence of recurrence of pleural effusion compared to TSP with placebo.
6. To determine if giving cathflo activase with TSP is associated with a lower incidence of pleural fluid loculations compared to TSP with placebo.
7. To determine if giving cathflo activase with TSP is associated with a shorter time to RSP in patients with MPE compared to TSP with placebo.
8. To determine if giving cathflo activase with TSP is associated with a shorter time to RSP in patients with benign pleural effusion compared to TSP with placebo.
9. To determine if giving cathflo activase with TSP is associated with any difference in pain as measured by a standard visual analog pain scale compared to TSP with placebo.
10. To determine if giving cathflo activase with TSP is associated with any difference in scoring on a visual analog scale for measurement of dyspnea compared to TSP with placebo.
11. To determine if giving cathflo activase with TSP is associated with shorter duration of chest tube drainage compared to TSP with placebo.
12. To determine if giving cathflo activase with TSP is associated with a short length of hospital stay after TSP compared to TSP with placebo.

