### **6.1. Sample Size**

Based on review of our experience with pleurodesis, TSP can be expected to produce RSP at three days in approximately 60% of patients. We anticipate an RSP rate of approximately 80% at three days using the combination of talc and cathflo activase. Therefore, in order to detect a 20% difference in successful pleurodesis with 80% power, a 5% significance level (1-sided) and 5% loss to follow-up, a total of 136 patients (68 in each arm) will be needed in this trial.

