## 8. PROCEDURES

Figure 1 shows the proposed workflow through the trial. Following the informed consent, each participant is assigned a unique study number and baseline data will be collected before randomization. At this point the research nurse will briefly explain the procedure and familiarize the participant with the Visual Analogue Scale (VAS) system for dyspnea (Appendix I) and pain (Appendix II). Trial treatment will be delivered by means of either a pigtail chest tube (size 10-14 Fr) or PleurX® catheter at bedside after randomization. Outcome measures will be assessed daily until the chest tube is removed and at routine follow-up visits at approximately 14 days, 28 days and three months after the day of procedure as outpatients if the patient has been discharged. While the chest tube is in place, daily symptom assessment will be performed, and daily chest x-ray (PA and lateral when possible) and 24-hour drain output will be recorded (Appendix III) to determine if RSP has been achieved, or if further intervention is indicated.

RSP is defined as chest tube drainage less than 100 cc over the previous 24 hours and a chest x-ray showing similar or decreased pleural space opacification compared to the baseline chest x-ray done the day of pleurodesis (day 0).

Objective determination of the chest x-ray finding will be based on the formal Radiology report in the medical record. If necessary, the findings will be clarified by personal communication between study personnel and the Radiologist reading the film. The algorithm for chest tube and pleural space management after TSP is specified in Figure 2. If RSP is not achieved on day 3, then management will be determined using the algorithm based on the chest x-ray findings and pleural drainage, and may include continued observation, repeat cathflo activase, chest CT, insertion of additional pleural drainage tubes, and repeat TSP with or without cathflo activase. At all follow-up visits after the chest tube has been removed, assessment will include chest x-ray and completion of the VAS for pain and dyspnea.

[figure not shown]
Figure 1. Proposed Workflow of the Trial

Assessments/tasks at visits:

- ◆ VAS scores for pain and SOB
- ◆ Drained volumes in 24 hours if the chest tube is still in place
- ◆ Serum hemoglobin if the chest tube is place
- ◆ CxR (PA and lateral)
- ◆ CT scan, as justified by the PI

Figure 2: Chest Tube Management Algorithm

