## 8.2. Assessments/Tasks

Following consent, a baseline assessment will be undertaken pre-randomization by a member of the trial team and entered into the REDCap system hosted at Office of Human Research of MHS. The following data will be recorded prior to randomization:

1. Patient demographics and physical characteristics
2. Mode of presentation, current diagnosis, cause of effusions (if known).
3. Medical history and current medication.
4. Previous pleural interventions.
5. Symptoms, including pain and SOB according to a visual analog scale (VAS) (Appendix I, II).
6. Pleural fluid biochemical and cytological test results
7. Baseline hemoglobin (day of or day before TSP)
8. Baseline (day of or day before TSP) CxR and chest CT (if available) findings.

After randomization and TSP with or without cathflo activase, all patients will have daily follow-up until the chest tube is removed, and at 14 and 28 days, and three months after TSP. At all visits, the following data will be recorded:

1. VAS for chest pain and SOB will be documented (Appendix I, II).
2. CxR (PA and lateral preferred).
3. Drained pleural volumes in 24 hours (if the chest tube is still in place).
4. Serum hemoglobin (only for inpatient visits within three days of the pleurodesis procedure).
5. Repeat pleural interventions.
6. Chest CT scan, as justified by the principal investigator.

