## 9.2. Statistical Analysis Plan

Statistical summaries and analyses of data will be performed at MHS. Descriptive analysis will be performed for all data including means and standard derivation or medians for continuous variables and proportions for categorical variables. Comparison of outcomes between the two arms will be performed using t-test for numerical variables and Pearson  $\chi^2$ -test or Fisher's exact for categorical variables, and a one-sided p-value of 0.05 will be considered to be statistically significant.

The main analysis for primary outcome will be performed as per the intention-to-treat principle, and will include all the randomized participants with an observed outcome.(26) The primary outcome of the success rate of pleurodesis at day 3 will be analyzed using  $\chi^2$ -test. Time to symptomatic fluid recurrence following initial successful pleurodesis within 3 months follow-up period will be analyzed using a log-rank test. An interim analysis will be performed by the Memorial Healthcare System Quality and Safety Steering committee under [name] (currently officially the DSMB for MHS) after 50 patients are randomized in order to test for efficacy. The O'Brien-Fleming stopping rule will be used, which requires a P value of < 0.0088 (1-sided) for the primary outcome in order to stop at the interim analysis. The O'Brien-Fleming rule requires a P value of < 0.05 (1-sided) at the final analysis in order to declare a statistically significant difference in the primary outcome.(27) Analyses will be performed with the use of Prism 7.0 or SPSS 26 software.

Costs will be those related to study medications, initial hospital stay, and subsequent hospitalizations. All costs will be reported in US dollars and in 2020 prices. Cost data for both

arms will be obtained from MHS Strategic Financial Support Services. Outcomes will be measured in terms of probability of treatment success and/or complication, and utility of health states, which will be transformed to quality-adjusted life years (QALYs), calculated as the success rate of pleurodesis from each patient at day 3 after administration of TSP combined with pain and dyspnea scores.

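### The only recurrence test named is restricted to patients who reach RSP, so it does not compare the randomised arms; the t-test rule applied to days to RSP has the same weakness

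*Combined protocol and SAP*

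**What the plan says.** Section 9.2 names one test for recurrence: "Time to symptomatic fluid recurrence following initial successful pleurodesis within 3 months follow-up period will be analyzed using a log-rank test". Section 9.1 defines successful pleurodesis as RSP, and RSP at day 3 is the primary outcome. Section 6.1 expects about 60% on talc alone and states "We anticipate an RSP rate of approximately 80% at three days using the combination of talc and cathflo activase".

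The recurrence hypothesis in section 4.2 carries no condition on success: "Reduces the incidence of recurrence of pleural effusion". Nor does objective 5, which asks whether the combination is "associated with a lower incidence of recurrence of pleural effusion compared to TSP with placebo". Recurrence is not among the nine secondary outcomes of section 9.1, and section 9.2 states intention-to-treat for the primary outcome only.

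Section 4.2 also hypothesises that the drug "Shortens the time to achieve pleurodesis". The matching outcome in section 9.1 is days to achieve RSP. Section 9.2 assigns numerical variables to a t-test and gives no rule for a patient who never reaches RSP. Section 9.1 separately lists the proportion with RSP at any time, so the plan does not presume that everyone gets there.

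**The concern.** A curve that starts at success contains only patients who succeeded, and treatment is meant to change who they are. If cathflo activase turns harder-to-treat patients into early successes, those patients appear in its curve and not in the control curve. The two curves then differ in case mix even if the drug does nothing to recurrence. A real reduction could be hidden, or the drug could look worse than it is. That matters here because section 3.1 itself raises the possibility that fibrinolysis could undo pleurodesis, and a spuriously poor recurrence curve would seem to confirm it.

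The word initial is also open. If RSP after day 3 counts, patients can enter the curve after further management, which section 8 says may include "insertion of additional pleural drainage tubes, and repeat TSP with or without cathflo activase".

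Days to RSP has the same structure. A mean among achievers says nothing about those who never achieve, so it can understate a real gain.

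**Working it through.** **The plan's own figure.** One-sided 5%, 80% power, 60% versus 80%, pooled variance: n = [1.645·√(2·0.7·0.3) + 0.842·√(0.24 + 0.16)]² / 0.2² = 63.9, so 64 per arm. Then 64/0.95 = 67.4, so 68 per arm and 136 in total, as stated. No size or power is stated for recurrence or days to RSP.

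**Who enters the curve on the day-3 reading.** 68·0.6 = 40.8 control and 68·0.8 = 54.4 cathflo patients. About 27 control and 14 cathflo patients are left out. This step needs no outside figure.

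**Assumptions, none from the documents.** 60% of patients succeed by day 3 on either arm, 20% only with cathflo activase and 20% on neither. Three-month recurrence is 15% in the first group and 15, 25 or 40% in the others. Recurrence times are exponential over 90 days, and each test is one-sided at 0.05.

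**Success-only test, no drug effect on recurrence**

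- Day-3 reading, 40% case: control 15%; cathflo (0.6·0.15 + 0.2·0.40)/0.8 = 21.25%. Apparent HR = ln(0.7875)/ln(0.85) = 1.47. The 25% case gives 17.5% and HR 1.18; the 15% case gives 1.00.
- Half of the day-3 failures reach RSP later and count, 40% case: control (0.09 + 0.08)/0.8 = 21.25%; cathflo (0.09 + 0.08 + 0.04)/0.9 = 23.33%; HR 1.11. The 25% case gives 1.05.

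**Simulated trials, 68 per arm**

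| Others' recurrence | 15% | 25% | 40% |
|---|---|---|---|
| False harm, success-only, day 3 | 5% | 9% | 19% |
| False harm, success-only, later RSP counted | 5% | 6% | 8% |
| False harm, all randomised, event possible in everyone | 5% | 5% | 5% |
| False harm, all randomised, never-RSP patients cannot have the event, no late RSP | 14% | 24% | 40% |
| Power at true HR 0.5, success-only, day 3 | 31% | 23% | 13% |
| Power at true HR 0.5, success-only, later RSP counted | 34% | 34% | 34% |
| Power at true HR 0.5, all randomised, event possible in everyone | 38% | 44% | 52% |

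The fourth row is a warning about the remedy. With never-RSP patients event-free, expected recurrence in the 40% case is 0.6·0.15 = 9% in control and 0.09 + 0.2·0.40 = 17% with cathflo activase. The HR is ln(0.83)/ln(0.91) = 1.98 with no drug effect at all.

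**Days to RSP.** Assume early RSP falls on days 2 to 3 (mean 2.5), late RSP on days 4 to 10 (mean 7), and the same share f of day-3 failures converts later in each arm. Achiever means are (0.6·2.5 + 0.4f·7)/(0.6 + 0.4f) in control and (0.8·2.5 + 0.2f·7)/(0.8 + 0.2f) with cathflo activase.

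| f | Means, control vs cathflo (days) | t-test power | All-randomised log-rank power |
|---|---|---|---|
| 0 | 2.50 vs 2.50 | 5% | 77% |
| 25% | 3.14 vs 2.76 | 37% | 72% |
| 50% | 3.63 vs 3.00 | 53% | 66% |
| 75% | 4.00 vs 3.21 | 64% | 64% |

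**The case against.** **Durability after success is a legitimate question.** Treatment failure has outcomes of its own in section 9.1 that are not limited to successes: RSP at day 3 and at any time, repeat pleurodesis, and additional chest tube. The general chi-square or Fisher rule could be applied to a recurrence proportion. This stands as a reason to keep the success-only curve. It does not supply a stated all-randomised recurrence comparison, because recurrence is not a listed outcome.

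**The larger figures need two things together.** These are the day-3 reading and a high assumed recurrence in the extra responders. If RSP at any time counts, false harm stays at 5 to 8%. This stands, and it limits the severity.

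**Restarting the clock at randomisation is not a cure by itself.** A reader might infer that it is. A patient whose fluid was never controlled cannot strictly recur. If such patients stay at risk but event-free, the comparison is more biased against cathflo activase than the present test. This stands in full and shapes the fix. The all-randomised error of 5% and power of 38 to 52% hold only if the event can also occur in those patients.

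**The days-to-RSP point is an inference.** The plan names no test for that outcome and does not say non-achievers are dropped. True, but the general rule assigns a t-test and only achievers have a value. A reader might go further and expect the better arm to look slower. With equal late conversion in the two arms this does not happen. On the illustration above, reversal needs 0.2·f(cathflo)/0.8 to exceed 0.4·f(control)/0.6. That means late conversion among cathflo failures more than 2.67 times that among control failures, and nothing in the documents suggests it.

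**Conclusion.** The concern holds. The named recurrence test selects on a post-randomisation outcome that treatment is planned to change, so it is not a randomised comparison and does not answer the recurrence hypothesis or objective 5. That conclusion needs no assumed rate. The size of the bias does, and the documents give none. On the rates assumed here it runs from zero, if the extra responders recur no more often than the others, to about 19% false harm on the day-3 reading.

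A reader might infer that the test invites false claims of benefit. If RSP improves as planned, the documents do not support that: the error runs against the drug. Only if cathflo activase lowered RSP would it run the other way. With the two rates exchanged, the same model gives false benefit in about 5, 9 or 19% of trials. Nor do the documents support a claim that recurrence results will necessarily mislead.

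Days to RSP is the lesser point: the t-test loses most when few failures convert later and nothing material at 75% conversion. Overall severity is minor to moderate. These are secondary analyses for which no power is stated, and the primary analysis is untouched.

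**What to change.** 1. **Time to RSP.** Analyse it from randomisation in all randomised patients, by cumulative incidence with a log-rank or Gray test. Keep non-achievers at risk to the end of follow-up, treat death as competing, and state whether RSP after repeat TSP counts.
2. **Success-only recurrence curve.** Keep it, define initial, and label it conditional and non-randomised.
3. **All-randomised comparison over three months.** Add one, and list it in section 9.1. Its event must be possible whether or not RSP was reached: symptomatic persistent or recurrent effusion on the treated side after removal of the first chest tube, or pleural re-intervention for it. Treat death as competing and report the components. Do not leave never-controlled patients in the risk set as unable to have an event.
4. **RSP without recurrence.** Show it separately as overall treatment success, since it partly re-counts the primary outcome.

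The cost is SAP wording, a written event definition and a few analyses. Section 8.2 already provides that "all patients will have daily follow-up until the chest tube is removed, and at 14 and 28 days, and three months after TSP", with symptom scores, chest x-ray and "Repeat pleural interventions" among the items recorded. The downside is that the new event mixes persistence with recurrence. The all-randomised and success-only analyses answer different questions, so both should be reported. The sample size and the primary analysis do not change.

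### The O'Brien-Fleming thresholds do not fit the planned look: 0.0088 belongs to a look at half the data, not at 50 of 136, and the final 0.05 is unadjusted, so the one-sided error exceeds 5%

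*Combined protocol and SAP*

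**What the plan says.** Section 9.2 (Statistical Analysis Plan) schedules one interim analysis "after 50 patients are randomized in order to test for efficacy". It names the O'Brien-Fleming stopping rule, "which requires a P value of < 0.0088 (1-sided) for the primary outcome in order to stop at the interim analysis", and adds that this rule "requires a P value of < 0.05 (1-sided) at the final analysis". The same section states that "a one-sided p-value of 0.05 will be considered to be statistically significant".

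Section 6.1 (Sample Size) is built on "a 5% significance level (1-sided) and 5% loss to follow-up" and concludes that "a total of 136 patients (68 in each arm) will be needed in this trial". The Abstract (section 2.0) repeats the look at 50 and the total of 136. Nowhere does the document give an information fraction, a spending function or an adjusted final significance level.

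**The concern.** A group-sequential rule fixes its interim and final thresholds jointly, and both depend on how much of the information is in hand at the look. Any chance of rejecting at the interim uses part of the 5%, so the final test must be run at slightly less than 5%. The plan pairs an interim level that looks like the half-way O'Brien-Fleming value with a final level that has not been reduced, and applies the pair to a look well before half-way.

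These two numbers are the whole decision rule for the primary outcome. If they are wrong, the trial does not hold its stated error rate. The monitoring committee would also be stopping on weaker evidence than the name O'Brien-Fleming implies, with about 25 patients per arm available for the safety and recurrence questions in section 4.2.

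**Working it through.** **Inputs**
- One-sided α = 0.05 (sections 6.1 and 9.2).
- Success rates 60% and 80%, power 80%, 5% loss, 136 patients, 68 per arm (section 6.1).
- Look at 50 patients; thresholds 0.0088 (z = 2.374) and 0.05 (z = 1.645) (section 9.2).
- Assumption: information is proportional to the number of patients with a day-3 outcome, so t = 50/136 = 0.368.

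**Step 1. The sample size reproduces.** With the pooled-variance formula and no continuity correction, n = [1.645·√(2·0.7·0.3) + 0.842·√(0.6·0.4 + 0.8·0.2)]² / 0.2² = 63.9, so 64 per arm. Then 64/0.95 = 67.4, so 68 per arm and 136 in total. The sample size is not the problem.

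**Step 2. Where 0.0088 comes from.** A two-look O'Brien-Fleming design rejects if Z₁ > C/√t at the interim or Z₂ > C at the end. C solves 1 − P(Z₁ < C/√t, Z₂ < C) = 0.05, with corr(Z₁, Z₂) = √t. At t = 0.5, C = 1.678 and C/√0.5 = 2.373, which gives p < 0.0088 and then p < 0.0467. Solving in reverse for the t that yields 0.0088 returns 0.4996. So the interim value is the half-information one, and the final value that belongs with it is 0.0467.

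**Step 3. Thresholds at the planned look, and the alternatives**

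| Rule | t | Interim p | Final p |
|---|---|---|---|
| Plan as written | 0.368 | 0.0088 | 0.05 |
| O'Brien-Fleming (z = 2.734, 1.657) | 0.368 | 0.0031 | 0.0487 |
| Lan-DeMets, O'Brien-Fleming type | 0.368 | 0.0012 | 0.0496 |
| Keep 0.0088, solve for the final level | 0.368 | 0.0088 | 0.0454 |
| O'Brien-Fleming, look at 68 patients | 0.5 | 0.0088 | 0.0467 |

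The Lan-DeMets interim level is 2[1 − Φ(1.960/√0.368)] = 0.0012. The stated interim level is 0.0088/0.0031 = 2.8 times the O'Brien-Fleming value and 0.0088/0.0012 = 7.3 times the Lan-DeMets value. Taking the final total as 128 (64 evaluable per arm, t = 0.39) gives 0.0039 and 0.0484, which does not rescue 0.0088.

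**Step 4. Type I error as written.** 1 − P(Z₁ < 2.374, Z₂ < 1.645) with correlation √0.368 is 5.44%. It is 5.42% at t = 50/128 and would be 5.32% even at t = 0.5. With the correct interim value of 0.0031 and the final level left at 0.05, it would be 5.13%.

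Exact binomial enumeration of the uncorrected χ² test (25 per arm, then 64, 65 or 68 per arm, common success rates 50% to 80%) gives 5.0% to 5.6%. The same final test without an interim gives 4.6% to 5.2%. The look therefore adds roughly 0.4 percentage points.

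**Step 5. Stopping and power at 60% versus 80%** (exact, 64 evaluable per arm)

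| Thresholds | Stop at 50 patients | Overall power |
|---|---|---|
| 0.0088 / 0.05 (as written) | 20% | 81.1% |
| 0.0031 / 0.0487 | 11% | 80.6% |
| 0.0012 / 0.0496 | 6% | 80.7% |

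**The case against.** The strongest reply is that the damage is small, and on the error rate that is fair. At the plan's own control rate of 60%, the exact error as written is 5.1% to 5.3%, against 4.7% to 4.9% with no interim. The final conclusion would change only if the one-sided p fell between roughly 0.045 and 0.05, with the lower end depending on the corrected pair chosen.

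Part of the exact 5.6% maximum also comes from the discreteness of the χ² test, which alone reaches 5.2%. The corrected pairs share this: their exact error runs from about 4.7% to 5.5%. They restore the nominal level; they do not guarantee 5% exactly.

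The result depends on the test version too. Section 9.2 does not say whether the χ² test is continuity-corrected. With a Yates correction or Fisher's exact test, the plan as written would stay below 5% (roughly 3% to 4%). The uncorrected test is, however, the natural reading and the one that reproduces the sample size; with a continuity correction, 74 per arm would be needed before allowing for loss.

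Finally, the factor of 7 is measured against Lan-DeMets spending, which the plan does not name. Against the named rule the factor is 2.8.

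These points limit the size of the problem. None of them makes 0.0088 the right value at 36.8% of the information or 0.05 the right final level, and no other section repairs either number.

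**Conclusion.** The concern holds. Both thresholds are wrong as written. The interim level belongs to a look at 50% of the information while the look is at 36.8%, and the final level takes no account of the alpha used at the interim. Saying that the rule calls for 0.05 at the end is incorrect at any look time, so that part does not depend on how the information fraction is counted.

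The overall one-sided error is 5.44% by normal theory, an excess of about 0.4 points. The more practical consequence is a chance of stopping at 50 patients of about 20% under the design assumptions, against 11% with the named rule. This rests on information proportional to patients with a day-3 outcome, equal arms (25 each at the look) and the uncorrected χ² test.

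The correction has to be made before interim data are seen, because thresholds revised afterwards are not credible.

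**What to change.** Replace both thresholds in section 9.2, in one of two ways:

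1. Keep the look at 50 patients and use Lan-DeMets O'Brien-Fleming-type spending, with boundaries recomputed at the actual information fraction. At 50/136 these are interim p < 0.0012 and final p < 0.0496, both one-sided. Staying with the original O'Brien-Fleming shape, 0.0031 and 0.0487, is equally valid at that fraction.
2. Move the look to 68 patients and use 0.0088 and 0.0467.

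Keeping 0.0088 at 50 patients would require a final level of about 0.0454, and the rule should then no longer be called O'Brien-Fleming.

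In every case, delete the statement that O'Brien-Fleming requires 0.05 at the final analysis, make the general one-sided 0.05 sentence subject to the adjusted level for the primary outcome, and state that the χ² test is uncorrected.

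Cost: wording in section 9.2 for the first option. The second also changes the Abstract and the monitoring schedule. The final test becomes slightly stricter. The 136 patients stand, with power of about 80% to 81% at 64 evaluable per arm.

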This protocol describes a prospective, randomized, double-blind controlled trial comparing TSP alone to the combination of TSP with cathflo activase for achieving optimal results with pleurodesis for recurrent pleural effusion. Patients who sign informed consent will be randomly assigned to receive either TSP alone (talc, 5 gm in 50 ml NS) with placebo (50 ml NS) or TSP with cathflo activase (4 mg in 50 ml NS) through the chest pleural catheter. Follow-up lasts for three months. The primary outcome is achievement of a “Radiographically Satisfactory Pleurodesis” (RSP) by day three post-procedure, defined as chest tube drainage of less than 100 cc over 24 hours *and* a chest x-ray showing similar or less pleural space opacification than on the day TSP was performed (baseline, day 0). Secondary outcomes include the proportion of patients who achieve RSP, time needed to achieve RSP, duration of chest tube drainage, length of hospital stay after initiation of TSP, proportion of patients requiring repeat TSP, change in serum hemoglobin during therapy, objective assessments of pain and dyspnea, and potential complications. The incremental cost effectiveness of talc slurry pleurodesis with cathflo activase compared to without cathflo activase will be assessed using a static decision tree model, which will be constructed using the TreeAge Pro software. This study will recruit 136 patients, with an interim analysis for efficacy after 50 patients, and aims to help develop the future standard for management of patients requiring pleurodesis for their symptomatic pleural effusion.

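### Cost-effectiveness analysis (9.2): costs run past day 3, but the success component of the effect is fixed at day 3

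*Combined protocol and SAP*

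**What the plan says.** The economic question is hypothesis 9 in section 4.2: that supplementation is as cost-effective as talc slurry alone. The Abstract (2.0) says that incremental cost-effectiveness "will be assessed using a static decision tree model". It gives neither a time horizon nor the branches of the tree.

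Section 9.2 then sets the two sides:

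- Costs: "Costs will be those related to study medications, initial hospital stay, and subsequent hospitalizations". There is no closing date.
- Effects: "Outcomes will be measured in terms of probability of treatment success and/or complication, and utility of health states". The utilities become QALYs, "calculated as the success rate of pleurodesis from each patient at day 3 after administration of TSP combined with pain and dyspnea scores". The visits at which those scores are taken, their weights and their conversion to utilities are not stated.

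Other sections describe what can happen after day 3. Under Procedures (section 8), a patient without RSP on day 3 may receive, among other options, "insertion of additional pleural drainage tubes, and repeat TSP with or without cathflo activase"; this applies to both arms. Section 9.1 makes RSP at any time a secondary outcome, and 9.2 plans a log-rank test of symptomatic recurrence over three months. Section 8.2 records "Repeat pleural interventions", a chest film and VAS scores at every visit up to three months.

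For the day-3 rates, section 6.1 states that "TSP can be expected to produce RSP at three days in approximately 60% of patients", and anticipates about 80% with cathflo.

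**The concern.** A cost-effectiveness comparison needs costs and effects counted over the same period. Here the cost window stays open after day 3, while the success term closes on day 3. Two kinds of patient are then misrepresented. One fails on day 3, is rescued as an inpatient and does well: the rescue is paid for and no success is recorded. The other succeeds on day 3 and is readmitted with recurrence: the readmission is paid for and the success stands.

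The plan expects twice as many day-3 failures in the control arm (40% vs 20%), so the mismatch need not cancel between arms. At stake is the answer to hypothesis 9. A treatment that only brings success forward, without making it last, could be reported as good value.

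**Working it through.** **1. The plan's own figure.** The documents state no cost-effectiveness figure. The one stated figure that uses the 60% and 80% rates is the sample size in 6.1. With one-sided alpha 0.05, 80% power, pooled variance and no continuity correction:

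n = [1.645 × √(2 × 0.7 × 0.3) + 0.842 × √(0.6 × 0.4 + 0.8 × 0.2)]² / 0.20² ≈ 63.9, so 64 per arm. Then 64 / 0.95 = 67.4, so 68 per arm and 136 in total. This matches the plan, so the two rates are used below as planned.

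**2. What 9.2 counts for each course of events.**

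| Course | Cost in 9.2 | Success term in 9.2 |
|---|---|---|
| Day-3 failure, inpatient rescue, later success | counted | 0 |
| Day-3 success, readmitted with recurrence | counted | 1 |
| Day-3 failure, outpatient rescue, later success | not clearly counted | 0 |

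**3. Size under the planned rates.** Let s be the day-3 success rate, r the share of day-3 failures who are effusion-free at three months after rescue, and q the share of day-3 successes who recur. Both r and q are assumptions, first taken as equal in the two arms.

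Three-month success = s(1 − q) + (1 − s)r

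Difference between arms = (0.80 − 0.60)(1 − q − r) = 0.20(1 − q − r)

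| r | q | Control | Cathflo | Three-month gain | Day-3 gain ÷ three-month gain |
|---|---|---|---|---|---|
| 0.3 | 0.1 | 0.54 + 0.12 = 0.66 | 0.72 + 0.06 = 0.78 | 12 points | 1.7 |
| 0.5 | 0.1 | 0.54 + 0.20 = 0.74 | 0.72 + 0.10 = 0.82 | 8 points | 2.5 |
| 0.7 | 0.1 | 0.54 + 0.28 = 0.82 | 0.72 + 0.14 = 0.86 | 4 points | 5 |

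If cathflo costs more, plain cost per success based on day 3 is too low by the factor in the last column. If q + r exceeds 1, the sign of the gain reverses.

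**4. Does the direction hold when the assumptions change?**

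- r = 0.25 control, 0.50 cathflo, q = 0: 0.70 vs 0.90, a gain of 20 points. No distortion.
- r = 0.25 control, 0.75 cathflo, q = 0: 0.70 vs 0.95, a gain of 25 points. Day 3 understates cathflo.
- r = 0.50 in both arms, q = 0.10 control, 0.20 cathflo: 0.74 vs 0.74. The gain is gone.
- Day-3 rates of 0.70 control and 0.60 cathflo, r = 0.50, q = 0: 0.85 vs 0.80. The day-3 difference of −10 points becomes −5, so day 3 tilts against cathflo.
- Equal day-3 rates, equal r and q: zero at both times.

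At 60% vs 80% with equal q, the distortion vanishes when 0.20(1 − q) + 0.20 × r(cathflo) − 0.40 × r(control) = 0.20, that is, when r(cathflo) = 2 × r(control) + q.

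**The case against.** The strongest reply is that the effect is more than day-3 success. The same sentence of 9.2 adds pain and dyspnea scores, and the one before it names complications and health-state utilities. VAS scores are collected through three months, so they could register a successful rescue or a recurrence. This stands in part: a reader might infer that the whole effect is frozen at day 3, and the documents do not support that. But without time points, weights or a mapping, nobody can say that the scores offset the mismatch. They also do nothing for the success term, which is expressly dated to day 3.

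A reader might also infer that the analysis is tilted toward cathflo whatever happens. The documents do not support that either. The direction depends on which arm has more day-3 failures and on rescue and recurrence rates in each arm, none of which is given. Section 3.1 itself allows that fibrinolysis could make pleurodesis fail. On the other side, the neutral condition at the planned rates needs rescue to succeed at least twice as often in the cathflo arm. That is impossible once control rescue success exceeds 50%, although the same rescue options are open to both arms.

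Three narrower replies stand. Objective 13 in section 4.2 compares hospital costs and has no effect denominator, so it is untouched. The three-month cost window is an inference, because 9.2 gives no end date. Outpatient rescue is not clearly among the listed costs, so it cannot be said that all rescue is paid for. Finally, RSP at any time and recurrence are analysed separately, so a short-lived effect would still be visible elsewhere in the results.

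**Conclusion.** The point holds for the success component. Section 9.2 counts cost beyond day 3 and fixes success at day 3, and the protocol expects rescue, later success and recurrence in between. Following the rule as written gives mismatched windows, so this is more than missing detail.

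Under the planned rates with r and q equal in both arms, the success term overstates cathflo's lasting gain: 20 points against 12, 8 or 4 in the cases shown. These figures are illustrations. They apply to the success term and to plain cost per success, and do not measure the error in the planned QALY result, which also depends on the unspecified VAS component. If cathflo both saves money and raises success, it stays dominant under either measure as long as q + r is below 1; only the size changes.

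The point bears on hypothesis 9 alone. The primary test, the sample size and the clinical secondary outcomes are unaffected. It should be corrected before the analysis, so that the horizon is not chosen after results are known.

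**What to change.** In 9.2:

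- Set one three-month horizon for both costs and effects.
- Make sure that the decision tree has branches for rescue and for recurrence.
- Define the effect from three-month status, using the film, recurrence and repeat pleural interventions already recorded under 8.2, together with VAS scores at the scheduled visits through three months. Give the weights and the mapping to utilities, the criterion for recurrence, and the handling of deaths and missing status.
- Include the cost of any recorded repeat pleural intervention, outpatient ones included, wherever its success is credited. Otherwise the change would create a mismatch in the other direction.
- Keep cost per day-3 success only as a secondary result, with costs cut at the same time point.

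The cost is SAP wording, possibly some added tree branches, and a unit cost for outpatient rescue. No new clinical data are needed. The downside is that three-month status will be missing for some patients and the effect will probably look smaller.
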